## **2 STUDY OBJECTIVES**

### **2.1 Primary Objectives**

The primary objectives of this study are:

- To assess the efficacy of 2 separate dose regimens (75 µg/kg and 225 µg/kg) of LR769 for the treatment of bleeding episodes in hemophilia A or B pediatric patients, from birth to <12 years old, with inhibitors to factor VIII or IX
- To assess the safety of LR769. This includes the immunogenic potential of the drug product

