### 3.1.2 Phase B (Treatment Phase)

Patients who complete Phase A will start with a treatment regimen that consists of 12-week periods of treatment with a certain dose. Depending on randomization, the treatment regimen will start with either 75 µg/kg or 225 µg/kg and patients will then cross over to the alternate treatment regimen every 12 weeks until the end of the study. From 24 hours after the administration of LR769 in Phase A, patients are eligible to be treated with LR769 in case they have a mild, moderate, or severe bleeding episode.

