### 3.1.2.2 Treatment of Mild/Moderate Bleeding Episodes

Treatment of a mild/moderate bleeding episode will be initiated as soon as possible but certainly within 4 hours of first symptoms of the bleeding episode. Treatment will consist of

an IV administration of either 75 µg/kg or 225 µg/kg of LR769 as a bolus injection administered in  $\leq$  2 minutes.

During the 75 µg/kg treatment regimen, the initial 75 µg/kg dose may be followed 3 hours later with 75 µg/kg every 3 hours until the bleeding is successfully treated. A maximum of 8 treatments in total are allowed in this treatment regimen for mild/moderate bleeding episodes.

During the 225 µg/kg treatment regimen, the initial 225 µg/kg treatment may be followed 9 hours later with 75 µg/kg every 3 hours until the bleeding episode is successfully treated. A maximum of 6 treatments in total are allowed in this treatment regimen for mild/moderate bleeding episodes.

If the bleeding episode is not successfully treated as assessed as an excellent or good response at 24 hours after the first administration, treatment with LR769 may not be continued and alternative treatment must be considered depending on the remaining symptoms (and be noted as concomitant medication). Treatment of this bleeding episode should not be continued with LR769 (study drug) in that case. The patient's physician may determine the best treatment in that case. This may be another bypassing agent [REDACTED]  
[REDACTED] or other hemostatic treatment.

Patients are allowed to be treated for another bleeding episode in a different anatomical location within 24 hours after initial start of treatment, provided the response to treatment of the initial bleeding episode was either "good" or "excellent". Occurrence of a bleeding episode in the same joint/anatomical location after 24 hours of the last treatment of the initial bleeding episode when an initial "good" or "excellent" response has been achieved will be treated as a new bleeding episode. If the bleeding episode occurs within 24 hours after the last treatment of the initial bleeding episode when an initial "good" or "excellent" response has been achieved, this is regarded a true recurrence and therefore a treatment failure. There is no restriction on the number of bleeding episodes that can be treated with LR769 for each patient in this study. The use of LR769 for prophylaxis is not permitted.

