## 9 PLANNED STATISTICAL METHODS

### 9.1 General Considerations

This section outlines the key components of the planned statistical analyses. Detailed methodology for the statistical analyses will be documented in a Statistical Analysis Plan (SAP). The SAP may modify the plan outlined in the protocol; however, any major modifications will also be reflected in a protocol amendment. If after database lock changes are made to the SAP, these deviations will be documented in the Clinical Study Report (CSR).

All data collected in this study will be documented using summary tables and patient data listings. Continuous variables will be summarized using descriptive statistics, specifically the sample size (n), mean, median, standard deviation, minimum and maximum. Categorical variables will be summarized by frequencies and percentages.

Where applicable, analyses will be done for all patients and by age group (aged from birth to  $<6$  years and  $\geq 6$  years to  $<12$  years).

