### 9.2 Determination of Sample Size

The proportion ( $\hat{p}$ ) of mild/moderate bleeding episodes treated with each dose of LR769 that are classified as being successfully treated will be compared with an objective performance criterion (OPC) of 0.55. A one-sided, one-sample normal approximation test, with an alpha = 0.0125 (adjusted from 0.025 to 0.0125 to account for multiplicity of testing), will be used to test the null hypothesis that  $p \leq 0.55$  versus the alternative hypothesis that  $p > 0.55$ , where  $p$  is the true proportion of mild/moderate bleeding episodes that are classified as successes. (Note: The standard error used in the denominator of the test statistic will account for the correlation among bleeding episodes for a given patient.) This will be done for each treatment regimen.

With the assumptions of a true proportion of success of 0.70, a correlation among bleeding episodes for a given patient of 0.1, and an OPC of 0.55, a sample size of 22 patients with a total of 352 mild/moderate bleeding episodes (assuming 8 bleeding episodes per treatment regimen per patient) will provide statistical power  $\geq 80\%$ . The study will enroll at least 24 patients, in order to account for dropouts and potential unevaluable bleeding episodes.

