The null hypothesis will be tested using a one-sided, one-sample, normal approximation test and a test statistic obtained by dividing ( $\hat{p} - 0.55$ ) by its estimated standard error, taking into account the correlation between bleeding episodes for a given patient. The test will be conducted at the 0.0125 level (adjusted from 0.025 to 0.0125 to account for multiplicity of testing). Treatment of mild/moderate bleeding episodes in the study with LR769 of a given dose will be regarded as successful if it is concluded that the true percentage of successfully treated bleeding episodes with that dose is greater than 0.55. The primary endpoint for the FDA is to satisfy the requirements of the US FDA for the evaluation of success.

No imputation of missing data will be performed for the primary analysis of the primary efficacy endpoint. However, two sensitivity analyses will be performed in order to examine the effect of missing data, if any, on the results of the primary analysis. In the first sensitivity analysis, all bleeding episodes for which the value of the primary efficacy endpoint is missing will be assigned as failures. In the second sensitivity analysis, all such bleeding episodes will be assigned as successes.

In addition, the proportions of successfully treated mild/moderate bleeding episodes will be compared between the two LR769 treatment doses at a 2-sided alpha of 0.05.

Two sensitivity analyses based on Generalized estimating equations (GEE) logistic regression analyses and Generalized linear mixed effects models (GLMM) will be used to assess the robustness of the result by accounting for the within-subjects correlation.

The primary efficacy endpoint for the EMA is defined as the proportion of bleeding episodes (mild/moderate and severe combined) with a “good” or “excellent” patient (for mild/moderate bleeding episodes) and physician (for severe bleeding episodes) reported assessment of efficacy at 12 hours after the first administration of study drug. This proportion of success will be evaluated by the EMA as part of the assessment of the benefit risk ratio for each dosing regimen.

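### The fixed 0.0125 split between the two dose tests is valid, but Holm's step-down would raise the chance that both doses succeed by about 8 to 9 points at the planning values

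*Protocol*

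**What the plan says.** Protocol 9.2 and 9.5.1 and the synopsis state the same rule. Each dose's proportion of mild/moderate bleeds successfully treated at 12 hours is compared with 0.55 by a one-sided normal approximation test: "The test will be conducted at the 0.0125 level (adjusted from 0.025 to 0.0125 to account for multiplicity of testing". Section 9.2 adds: "This will be done for each treatment regimen". The verdict is given dose by dose: "Treatment of mild/moderate bleeding episodes in the study with LR769 of a given dose will be regarded as successful" if that dose's own test rejects. The first primary objective (2.1) covers both regimens: "To assess the efficacy of 2 separate dose regimens".

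The documents do not use the name Bonferroni, but 0.025/2 = 0.0125 is that split. Neither the protocol nor the SAP addendum contains a step-down rule or a reason for preferring the fixed split. Power is stated per dose only; none is given for both doses succeeding.

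**The concern.** Under the fixed split, a dose with a one-sided p-value between 0.0125 and 0.025 fails even when the other dose has clearly passed. Section 9.5.1 also reports a 95% confidence interval for each dose, and its lower limit corresponds to one-sided 0.025. Such a dose would therefore have an interval lying wholly above 0.55 and still be called unsuccessful.

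Holm's procedure tests the smaller p-value at 0.0125 and, if that rejects, tests the other at 0.025. It needs no assumption about how the two dose estimates are correlated. That matters here because the same patients supply both doses: "patients will then cross over to the alternate treatment regimen every 12 weeks until the end of the study". In a trial of about 24 children the extra power costs no patients and no data.

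**Working it through.** **Inputs (Protocol 9.2).** Null rate 0.55; true rate 0.70; within-patient correlation 0.1; 22 patients; 8 bleeds per patient per regimen, so 176 per dose; one-sided 0.0125.

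**Step 1: the plan's own figure.** Design effect = 1 + 7 × 0.1 = 1.7. SE = √(0.70 × 0.30 × 1.7/176) = 0.0450.

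- At 0.0125: A = 0.15/0.0450 − 2.241 = 1.089, power Φ(A) = 86.2%.
- At 0.025: B = 0.15/0.0450 − 1.960 = 1.371, power Φ(B) = 91.5%.

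The stated power of at least 80% holds. With the null SE (0.0489) in the critical value it is 81.5%, but 9.5.1 divides "by its estimated standard error, taking into account the correlation between bleeding episodes for a given patient", so the 86.2% version fits the test as written.

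**Step 2: chance that both doses succeed.** With r the correlation between the two test statistics:

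- Fixed split: Φ₂(A, A; r).
- Holm: 2Φ₂(A, B; r) − Φ₂(A, A; r).

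The documents do not give r. It is taken from 0 (no shared patient effect) to 8 × 0.1/1.7 = 0.47 (the 0.1 also holds across doses). At r = 0 the fixed split gives 0.862² = 0.743, and Holm gives 2 × 0.862 × 0.915 − 0.743 = 0.834.

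| | r = 0 | r = 0.47 |
|---|---|---|
| Both, fixed split | 74.3% | 77.3% |
| Both, Holm | 83.4% | 84.9% |
| Gain | 9.1 points | 7.6 points |
| Per dose, fixed split | 86.2% | 86.2% |
| Per dose, Holm | 90.7% | 90.0% |
| At least one, either rule | 98.1% | 95.1% |

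**Step 3: other true rates.** With 0.65 and 0.70, the chance of both goes from 39.4% to 51.4% (r = 0) or from 43.3% to 54.4% (r = 0.47). With 0.75 in both doses the gain is under 1 point, and at 0.80 it is nil.

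**Step 4: error for one ineffective dose when the other has rate 0.70.** Fixed split: 0.0125. Holm at r = 0: 0.0125 + 0.0125 × 0.862 = 0.0233; at r = 0.47, 0.0249. Both stay within 0.025.

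**Step 5: simulation.** The closed form treats the SE as known. The check drew beta-binomial patient effects with 8 bleeds per regimen and estimated the SE from the 22 patient means. That SE is an assumption, because the protocol gives no formula. The normal critical value was kept.

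| | No sharing | Full sharing |
|---|---|---|
| Both succeed, fixed split to Holm | 68.8% to 78.4% | 72.3% to 80.6% |
| Wrong pass of one ineffective dose | 0.020 to 0.032 | 0.020 to 0.034 |
| Family error, both doses ineffective (either rule) | 0.040 | 0.038 |

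The levels are about 5 points lower than in Step 2, but the gain is still 8 to 10 points. At a true rate of 0.75 the simulated gain is about 2 points.

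**Step 6: unequal bleed counts.** Section 3.1.2.2 sets no cap: "There is no restriction on the number of bleeding episodes that can be treated with LR769 for each patient in this study". With assumed gamma-Poisson counts (mean 8, underlying CV 0.5) and a cluster-robust SE, the chance of both goes from 60.1% to 70.2% (no sharing) or from 64.1% to 73.0% (full sharing). Wrong pass goes from 0.024 to 0.037 or from 0.025 to 0.040, against a both-ineffective family error of 0.050 or 0.047.

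**The case against.** The plan contains no error here: the split is valid, it is stated consistently, and a protocol need not justify leaving out a sharper procedure. Success of both doses is not a study criterion. On the protocol's own per-dose criterion the gain is about 4 to 5 points, on power that already meets its target. All of this stands, and it is why the point is optional.

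The stronger objection concerns error. With 22 patients and a normal reference, the fixed split leaves a margin: if only one dose works, the other wrongly passes in about 2.0% of simulated trials, below 2.5%. Holm uses that margin and takes the figure to 3.2-3.4%. This also stands. However, the excess comes from the normal approximation with few clusters. When both doses are ineffective, the planned split already has a family error of 3.8-4.0%, and Holm leaves that unchanged.

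Two further limits apply. Section 9.1 allows "The SAP may modify the plan outlined in the protocol", and the main SAP (version 2.0) was not supplied, so it may already settle the matter. The trial is also open-label with DMC review of efficacy data (9.11), so loosening the second threshold after results are known would be hard to defend.

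**Conclusion.** The point holds as an efficiency suggestion of low severity. For the test as written, Holm adds 7.6 to 9.1 points to the chance that both doses succeed, and about 4 to 5 points to per-dose power. It adds nothing to the chance that at least one does. These figures rest on the protocol's planning values and on a between-dose correlation of 0 to 0.47. The gain is larger if one dose is somewhat weaker, and it disappears if both true rates are near 0.80. Control of the nominal 0.025 family level does not depend on the correlation.

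**What to change.** In 9.2, 9.5.1 and the synopsis, replace the fixed level by a rule of this kind: *the smaller of the two one-sided p-values is tested at 0.0125; if it is rejected, the other is tested at 0.025 (Holm).* Check main SAP version 2.0 first, and make the change only before outcome data are reviewed. If the fixed split is kept, state why.

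The cost is wording, the higher wrong-pass chance for a single ineffective dose given above, and simultaneous intervals that are less simple than those matching a fixed split.

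The small-sample excess of the normal test is a separate matter that this change does not repair. If a t reference with 21 degrees of freedom were adopted together with Holm, the simulated chance of both would be about 74% (no sharing) or 77% (full sharing). That is a net gain of about 4 to 5 points over the planned test, and the chance of at least one success would fall by about 2 points.

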#### 3.1.2.4      Rescue Treatment

In case of an insufficient effect of LR769 (e.g., insufficient effect after 24 hours for a mild/moderate bleeding episode, or continued excessive bleeding in a severe bleeding episode), the treating physician should stop treatment with LR769 and treat the patient with another therapy, such as the treatment they used prior to enrollment in this study. This may be another bypassing agent [REDACTED] or other effective hemostatic treatment. The patient can return to treatment with LR769 for a new bleeding episode provided that at least 24 hours has passed since the other bypassing agent was given.

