## **5.6 Concomitant Therapy**

Restrictions to concomitant therapies are limited to the use of other sources of FVII(a), such as aPCC (FEIBA®) or NovoSeven®. These products must be avoided if at all possible, and may only be used for rescue therapy, in the event of an insufficient response to the study drug.

Other agents in the treatment of a bleeding episode, such as antifibrinolitics (e.g., aminocaproic acid or tranexamic acid) are allowed.

Patients on ITI therapy with FVIII or FIX products are allowed to be treated in the study as well, i.e., patients under this regimen are not excluded from the study, as long as they fulfill the criteria for inhibitors and frequency of break-through bleeding episodes as described in the inclusion criteria.

All concomitant medications need to be registered in the patients' files and/or patients' diaries and recorded in the eCRF.

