## 9.5 Primary Endpoint

### 9.5.1 Primary Efficacy Endpoint

The primary efficacy endpoint for this study is defined as successful treatment of a bleeding episode at 12 hours after first administration of the study drug. The following are clarification definitions to satisfy regulatory requirements in multiple regions (i.e., the FDA and the EMA).

For primary efficacy endpoint for the FDA, only mild/moderate bleeding episodes are taken into account. Severe bleeding episodes will be a minority of the bleeding episodes treated in the study, and require further treatment even if the bleeding has improved. Efficacy in severe bleeding episodes will be analyzed separately, using descriptive statistics only.

The primary efficacy endpoint for the FDA is defined as the successful treatment of a bleeding episode at 12 hours (bleeding episode level), where a success is defined as meeting all of the following criteria:

- *Good or Excellent* response noted by patient/parent/guardian, depending on patient's age and maturity
- Study drug treatment: No further treatment with study drug beyond timepoint where a Good or Excellent response for this bleeding episode was noted
- No other hemostatic treatment needed for this bleeding episode
- No administration of blood products indicating continuation of bleeding beyond timepoint where a Good or Excellent response for this bleeding episode was noted
- No increase of pain beyond timepoint where a Good or Excellent response for this bleeding episode was noted that cannot be explained other than as continuation of bleeding

For each LR769 treatment, the proportion ( $\hat{p}$ ) of mild/moderate bleeding episodes rated as successfully treated at 12 hours will be summarized using the count and percentage. A 95%

normal approximation CI for the true percentage will be calculated taking into account the correlation between bleeding episodes for a given patient in calculating the standard error of the estimate  $\hat{p}$ .

The null and alternative hypotheses for the primary efficacy endpoint are as follows:

$$H_0: p \leq 0.55$$

$$H_1: p > 0.55.$$

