## 9.6 Secondary Endpoints

The secondary efficacy endpoints consist of the following:

- Proportion of mild/moderate bleeding episodes successfully treated according to the same criteria as the primary endpoint of efficacy, at all other timepoints

- Proportion of bleeding episodes (mild/moderate and severe, separately and combined) with a “good” or “excellent” patient (and/or physician when available) reported assessment of efficacy at all timepoints
- Time to assessment of a “good” or “excellent” response of the bleeding episodes (mild/moderate and severe, separately and combined) by the patient (and/or physician when available)
- Descriptive analysis of the number of administrations and mean total amount of drug administered per bleeding episode

For each treatment regimen and both treatment regimens together, the proportions of bleeding episodes successfully treated, according to the same criteria as the primary endpoint of efficacy at all timepoints will be summarized using descriptive statistics, and a 95% CI for the true mean patient level proportion will be calculated based on normal approximation.

For each treatment regimen and both treatment regimens together, the proportions of bleeding episodes with a “good” or “excellent” patient reported assessment of the efficacy at all timepoints will be summarized using descriptive statistics, and a 95% CI for the true proportion will be calculated based on normal approximation.

The time to assessment of a “good” or “excellent” response of the bleeding episodes (mild/moderate and severe, separately and combined) by the patient/parent will be analyzed at the bleeding episode level using the K-M method to estimate the survival distribution for this endpoint for each treatment regimen separately and combined. Patients who receive rescue treatment at any time will be considered failures and will be assigned a censored value at the final timepoint. Patients who do not achieve a “good” or “excellent” response will be censored at the time of last response.

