## Phase B - Treatment of Mild/Moderate Bleeding Episodes

Evaluation	Mild/Moderate Bleeding Episode									
	Pre-treatment	0 hrs	3 hrs	6 hrs	9 hrs	12 hrs	15 hrs	18 hrs	21 hrs	24 hrs
Bleeding Characteristics 	X									
Drug Administration 		X	X 	X 	X	X	X	X	X	
Efficacy Assessment 			X	X	X	X 	X	X	X	X 
Patient Diary 	X	X	X	X	X	X	X	X	X	X
AE Assessment	Throughout Study									
Conmed Assessment	Throughout Study									

 Includes location, date, time of start of bleeding, severity, spontaneous or traumatic

 Exact date, time and dose administered to be noted for each administration

 No study drug administration when in the 225 µg/kg treatment regimen

 Before each (planned) study drug administration and 3 hours after last

 Always to be done, regardless of study drug administration

 By the parent(s)/guardian or other caregiver in conjunction with the patient where possible (e.g., depending on age). Additionally, the site staff will collect their assessment in the patient's records (if applicable).

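### The EMA primary endpoint and the good/excellent proportions have no rule for rescue before the rating, so a rescued bleed can count as an LR769 success

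*Protocol*

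**What the plan says.** **The endpoint.** Protocol Section 9.5.1 bases the EMA primary endpoint on a good or excellent "reported assessment of efficacy at 12 hours after the first administration of study drug. This proportion of success will be evaluated by the EMA". The patient or parent rates mild/moderate bleeds and the physician rates severe ones. The Synopsis and Section 6.8.1 give the same definition. None of these places mentions rescue. The secondary good/excellent proportions at all timepoints (Section 9.6) and the tertiary physician rating at 12 hours (Section 9.7) have no rescue rule either. SAP addendum Section 2 repeats these proportions without adding one.

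**When rescue can happen.** Section 3.1.2.4 gives two examples. For severe bleeds it is "continued excessive bleeding in a severe bleeding episode), the treating physician should stop treatment with LR769 and treat the patient with another therapy", with no minimum time. For mild/moderate bleeds it is "insufficient effect after 24 hours for a mild/moderate bleeding episode". Section 5.6 says other FVII(a) products "may only be used for rescue therapy, in the event of an insufficient response to the study drug", also with no time limit.

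**When the rating is made.** Section 6.8 makes the 12-hour rating mandatory for every bleed and counts it from the first dose. For mild/moderate bleeds, Appendix 1 adds "Always to be done, regardless of study drug administration".

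**How rescue is scored elsewhere.** One FDA success criterion in Section 9.5.1 is "No other hemostatic treatment needed for this bleeding episode". For time to response, which covers severe bleeds, Section 9.6 says "Patients who receive rescue treatment at any time will be considered failures and will be assigned a censored value at the final timepoint".

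**Antifibrinolytics.** Section 5.6 says: "Other agents in the treatment of a bleeding episode, such as antifibrinolitics (e.g., aminocaproic acid or tranexamic acid) are allowed".

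**The concern.** The first primary objective is the efficacy of LR769. If another bypassing agent is given at hour 4 and the bleed is rated good at hour 12, the rating reflects both products or mainly the second. The EMA definition, followed as written, has no condition that stops this bleed from counting as a success.

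Two things are at stake. First, any error favours LR769. Second, the plan would treat the same event in two ways: a rescued severe bleed could be a success in the EMA proportion and a failure in the time-to-response analysis of the same bleeds.

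**Working it through.** **1. The plan's own figure.** The only stated operating characteristic is power of at least 80% per regimen for the FDA endpoint (Section 9.2). The inputs are 22 patients, 8 mild/moderate bleeds per regimen per patient, correlation 0.1, true rate 0.70, criterion 0.55 and one-sided alpha 0.0125.
- Design effect: 1 + (8 − 1) × 0.1 = 1.7.
- Effective n per regimen: 22 × 8 / 1.7 = 103.5.
- Power: 81.5% with the null variance in the critical value, 86.2% with the alternative variance.

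Both agree with the stated figure. The EMA endpoint has no test, threshold or power statement, so nothing here changes.

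**2. Direction.** Take a bleed rescued before 12 hours.
- Rated none or moderate: a failure with or without a rescue rule.
- Rated good or excellent: a success as written, a failure if rescue is scored as failure.
- Not rated: if missing values are not imputed, the bleed leaves the denominator; with an explicit rule it is a failure.

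The first case is neutral and the other two favour LR769.

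**3. Size when the rating is made.** Let r be the share of bleeds rescued before 12 hours and g the share of those rated good or excellent. The inflation is r × g. The documents give neither quantity.

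Suppose early rescue occurs only in severe bleeds. Let s be the severe share of all bleeds and q the share of severe bleeds rescued early, so r = s × q. Assumed ranges: s 2% to 10%, q 10% to 30%, g 0.5 to 0.9.
- Combined proportion, s × q × g: from 0.02 × 0.10 × 0.5 = 0.1 point to 0.10 × 0.30 × 0.9 = 2.7 points.
- Severe-only proportion, q × g: from 0.10 × 0.5 = 5 points to 0.30 × 0.9 = 27 points.

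A count-based illustration for one regimen uses the planned 176 mild/moderate bleeds (22 × 8) and an assumed 10 severe bleeds, of which 2 are rescued early and then rated well. The severe-only proportion rises by 2/10 = 20 points and the combined proportion by 2/186 = 1.1 points.

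**4. Size when the rating is missing.** With S successes among n bleeds, k of them rescued and unrated, the inflation is S/(n − k) − S/n. For n = 10, k = 2, S = 6 (all assumed), this is 6/8 − 6/10 = 75% − 60% = 15 points in the severe-only proportion.

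**5. Which analyses conflict.** Severe bleeds are outside the FDA endpoint, so for them the EMA proportion conflicts only with the time-to-response analysis. An EMA/FDA conflict needs a mild/moderate bleed rescued before 12 hours. The example in Section 3.1.2.4 places that rescue after 24 hours, so this is possible but not the described path.

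**The case against.** **No sentence credits rescued bleeds to LR769.** A reader might infer that the plan does so. It does not say so; it is silent. Section 9.1 leaves detailed methods to the SAP, and only an addendum to the main SAP (version 2.0) is available here, so a rule may exist there. This stands, and it limits the claim to what the protocol definition permits.

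**The rating scale may guard against it.** Section 6.8 attributes the improvement to the treatment and refers to the need for more study drug. A physician who has just stopped LR769 for lack of effect could rate it none or moderate. This stands in part, but nothing tells the rater how to score a bleed after a switch.

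**A severe bleed may not be rated after LR769 stops.** Section 7.2.2.4 places the 12- and 24-hour ratings under continued treatment, and the Appendix 1 table for severe bleeds ties ratings to planned study drug doses. This conflicts with the mandatory 12-hour rating in Section 6.8. It does not remove the problem: the value may then be missing. Section 9.5.1 does plan a sensitivity analysis with missing values as failures, but it is set out with the FDA analysis and is not expressly extended to the EMA proportion.

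**Rescue is visible elsewhere.** Section 9.7 reports the proportion of bleeds needing another treatment, and time to response counts rescue as failure. Both help a reader, but neither corrects the success count.

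**The two regional definitions differ on purpose.** This is true, and the EMA endpoint need not adopt every FDA criterion. It still needs its own rule for rescue.

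**Conclusion.** The concern holds as a gap in the definition. As written, the EMA primary endpoint and the good/excellent proportions can count a bleed rescued before the rating as an LR769 success, or lose it as missing, and both favour LR769.

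With early rescue confined to severe bleeds, the bias is about 0.1 to 2.7 points in the combined proportion and 5 to 27 points in the severe-only proportion. All the rates behind these ranges are assumed.

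Three stronger readings are not supported:
- That one severe bleed could be an EMA success and an FDA failure. Severe bleeds are not in the FDA endpoint.
- That the combined proportion is inflated by many points. That would need frequent early rescue in mild/moderate bleeds, which is not the described path.
- That the primary test is affected. The test belongs to the FDA endpoint, which already excludes bleeds needing other hemostatic treatment.

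Antifibrinolytics are a separate ambiguity. Section 5.6 permits them, and the FDA criterion does not say whether they count as other hemostatic treatment.

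**What to change.** In the Synopsis and Sections 6.8.1, 9.5.1, 9.6 and 9.7, and in the main SAP if it has no such rule, state for the EMA endpoint and every good/excellent proportion that:
- an episode given rescue or alternative hemostatic treatment before a rating is a failure at that and all later timepoints;
- it stays in the denominator even if the later rating is missing;
- the as-rated proportion is reported as a sensitivity analysis.

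Do not make antifibrinolytics failures by default. Reconcile Section 5.6 with the FDA criterion in Section 9.5.1, state once how they are classified for scoring, apply that to both definitions, and run the other classification as a sensitivity analysis. Also reconcile Sections 6.8 and 7.2.2.4 and Appendix 1 on whether a severe bleed is rated at 12 hours once LR769 has stopped.

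The cost is a few sentences and one extra set of tables. Section 6.8 already collects the nature and the start and stop times of alternative treatment for each bleed, so no new data are needed. If the database is already locked, Section 9.1 requires the change to be documented in the study report. The EMA proportion may become slightly less favourable. The change concerns scoring only and leaves patient management as it is.
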